[name]

[name]

[name]

Statisticians: [name]

[name]

Study Management:

For general queries, supply of study documentation, and collection of data, please contact:

Study Coordinator: [name]

Address: Centre for Health Services Studies

University of Kent

Canterbury

[name]

[contact]

E-mail: [contact]

Clinical Queries should be directed to [name], Project Manager, who will direct the query to the appropriate person

For further information regarding the sponsorship conditions, please contact the University of Kent, Research Ethics and Governance Officer, [name] ([contact])

This protocol describes the OPEL H@H study and provides information about procedures for entering participants. Every care was taken in its drafting, but corrections or amendments may be necessary. These will be circulated to investigators in the study. Problems relating to this study should be referred, in the first instance, to the Chief Investigator. This study will adhere to the principles outlined in the NHS Research Governance Framework for Health and Social Care (2nd edition). It will be conducted in compliance with the protocol, the Data Protection Act and other regulatory requirements as appropriate.

STUDY SUMMARY

TITLE Optimum Hospice at Home Services for End-of-Life care

DESIGN Realist approach utilising mixed methods research

AIMS 1. Assess the impact of hospice at home (H@H) care models on

patient and carer outcomes

2. Investigate the resource implications and costs of patient care in

different H@H care models

3. Explore the experiences of patients, family carers, providers and

commissioners of the different H@H models

4. Identify the enablers and barriers to embedding H@H models as

part of service delivery

QUANTITATIVE OUTCOMES Quality of Death (QODD survey)

Holistic patient assessment (iPOS tool)

Assessment of care by bereaved relatives (VOICES survey)

Ambulatory and Home Care Record (AHCR)

POPULATION Patients receiving Hospice at Home services

Carers of participants receiving H@H care

Stakeholders, commissioners and service providers of H@H services

DURATION 3 years

Study summary diagram

[figure not shown]

Table of Contents

STUDY CONTACT DETAILS	14
STUDY SUMMARY	15
GLOSSARY OF ABBREVIATIONS	17
KEYWORDS	17
1. INTRODUCTION	18
2. STUDY OBJECTIVES	19
3. STUDY DESIGN	19
4. STUDY SITES	20
5. PARTICIPANT ENTRY	21
5.1 PATIENT CONSENT	21
5.1.1 INCLUSION CRITERIA	22
5.1.2 EXCLUSION CRITERIA	22
5.2 CARER CONSENT	22

1. INTRODUCTION

Hospice at home (H@H) services aim to offer the quality and ethos of hospice care at home to support dying patients to have a "good death". H@H services provide patients with choice about where they receive their care at the end of life which is central to UK policy [1]. While the majority of people would wish to die at home [2] and the evidence indicates that the number of people expressing this wish is increasing [3-5], health and social care services are ill-equipped to meet this demand [6]. Identifying how care can be delivered and maintained at home was identified as a top ten priority by the James Lind Alliance in 2015 [7]. Currently the evidence for H@H services is mixed, with wide variation in service provision and the settings in which they operate. Services which have been evaluated often demonstrate positive benefits for patients, such as increased choice and death at home [8-13], though not all H@H services demonstrate the same outcomes. It is unclear what elements of these services deliver which outcomes and to what extent such outcomes are delivered in conjunction with other primary care and community services which form part of the care that end of life patients receive. Lack of clarity around what aspects of services produce which outcomes makes sharing good practice between H@H services difficult and stifles efficient service development. To address this knowledge gap, we are conducting a multi-site evaluation with methods that are able to capture in depth the structure, process and outcomes which can inform national policy and commissioning decisions to provide optimum H@H services.

In 2007, Pilgrims Hospices, which operated 3 inpatient hospices along with a community nursing service, decided to increase community provision to enable more patients to die in their own homes in response to feedback from patients and families. In order to ensure that these service changes were in line with the best available evidence, Pilgrims Hospices commissioned a literature review of the evidence for H@H services which was carried out at the University of Kent. The literature review [8] indicated that the evidence base for the efficacy of such services was weak with few controlled studies, though many qualitative studies indicated that such services were appreciated by patients and their families. Characteristics of services which appeared to produce the most favourable outcomes included: care given by palliative care specialists, out-of-hours availability, crisis intervention and rapid response capability. Based on the findings from the literature review, the hospice designed a new hospice at home service with the following features: senior healthcare assistant (HCA) led with specialist training given by the hospice, available 24/7 at 4 hours' notice, to support dying at home and families in crisis, supported by the full hospice multidisciplinary team and existing community services, and designed to add benefit by fitting around existing services. An evaluation alongside the roll out of this service was planned, in collaboration with the University of Kent, to contribute to the weak evidence base identified in the literature review. The evaluation used a quasi-experimental, cluster design and the results have been published [9-10]. We found that the new service did not improve patients' chances of dying in their preferred place (over 60% of patients were able to die in their preferred place in both intervention and control groups), though patients in areas where the hospice at home service was operating had a significantly higher preference to die at home.

From the results of this study, a number of questions remain unanswered. Is there a better service configuration than the one examined here which would allow more patients to die where they want? How does the availability of hospice at home influence patient preferences? One of the gaps with this service was difficulty in access to medications which was in part due to challenges in working with other community providers; how can we improve this with our partners in the community? Around 60% of our patients die where they want to; what would be the highest level we could hope to achieve, i.e. what is a realistic gold standard and what services are able to deliver this? Our collaboration with the National Association for Hospice at Home (NAHH) on this project confirms that these questions, and the overall question of what does an optimal hospice at home service look like, are commonly debated across the end of life care sector. These service development issues faced by

Pilgrims Hospices serve as an example and a snapshot of the national problem of how best to develop hospice at home services.

The variation in services and the settings in which they operate makes traditional comparative analyses difficult to do to achieve a meaningful synthesis of evidence which would help to inform service development and planning. In addition to there being little understanding of what the key features of H@H services are that deliver desirable outcomes, the range of H@H services in existence makes it difficult to identify similar services in comparable settings. There are 132 H@H adult services listed in the Hospice UK directory (search 16/07/2014), yet there has been little consensus as to what standards characterise such a service or what makes a service more or less effective. Services differ in terms of structure, functioning and access around the country. The National Association for Hospice at Home (NAHH) have recommended six core, national standards for H@H services developed through three national H@H stakeholder workshops held in 2011-12 [14]. The NAHH also worked with Hospice UK and conducted a survey across 76 H@H services in England, which provided some useful data to start to describe the landscape of H@H services. This survey concluded that more than one model of H@H service exists and they are not homogenous in their outcomes [15].

2. STUDY OBJECTIVES

The aim of this proposed study is to investigate the impact of the organisation and delivery of different models of H@H on patient and carer outcomes and experiences of end of life care.

Our research question is:

What are the features of H@H models that work, for whom, and under what circumstances?

The study objectives are to:

- 1. Assess the impact of service models and settings on patient and carer outcomes.
- 2. Investigate the resource implications and costs of patient care in each model.
- 3. Explore the experiences of patients, family carers, providers and commissioners of the different models.
- 4. Identify the enablers and barriers to embedding H@H models as part of service delivery.

3. STUDY DESIGN

Our research design is informed by realist evaluation [16-17] that will be used to identify candidate programme theories that will be tested and refined throughout the proposed research in order to address our objectives. The funded programme of research will be conducted in 3 phases. This protocol outlines the research and processes for Phase 2 and subsequent Phase 3 consensus events (section 8.5).

Phase 1: Survey

A national telephone survey will be conducted of all known H@H services in the Hospice UK service directory to map the range and variation of H@H services in order to develop a typology of models. This phase has received HRA approval (HRA ref # 17/HRA/0299).

Phase 2: Case studies.

To ensure maximum range, we will purposively select up to 8 case studies of H@H services that vary in model 'type' and location (1-2 case studies per model). 66 patients per model type will be recruited and tracked over time (until death) through data collection from the service provider and the patient's

carer. The primary outcome will be the quality of death and will be collected post death. This will be collected using the Quality of Dying and Death (QODD) tool, a validated interview instrument conducted with bereaved carers [18-20]. Secondary outcomes will include holistic patient assessment (iPOS) [21] and assessment of care by bereaved relatives (VOICES) [22] and service use (AHCR) [23]. Regression analysis will be used to isolate the impact of each service model on quantitative outcomes. An embedded economic analysis will capture resource use and calculate costs. Barriers and enablers to service provision will be explored through in depth interviews with carers, commissioners and providers. Analysis will be iterative with the aim of testing and refining programme theories and to develop provisional context-mechanism-outcome (CMO) configurations. Normalisation Process Theory (NPT) [24] will be used to understand why a model has or has not been embedded within a whole system of care.

[figure not shown]
Phase 3: National consensus workshops.

Provisional CMO configurations will be presented and discussed with stakeholders in two workshops to validate interpretation of the data and to refine our understanding of what works, for whom, and under what circumstances. Guidelines will be developed for services and commissioners to help develop H@H services matched to local needs. The most appropriate format for this guidance (e.g. menu of service elements, setting characteristics etc.) will be identified through the consensus events.

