6. DATA COLLECTION AND FOLLOW-UP

6.1 PATIENTS

After consent, a member of the participants direct care team will collect some background information about the patient, the Integrated Palliative Care Outcome Scale (iPOS) questionnaire (staff version), phase of illness and modified Karnofsky score. These data will be collected at the point of entry to the H@H service or within 24 hours of consent. The patient and carer pathway is laid out in Figure 2 below.

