6.2 CARERS

After consent, a member of the research team will contact the carer as soon as possible to collect health service use data retrospectively for up to two months prior to recruitment. This data will be collected using the Ambulatory and Home Care Record (AHCR) that has been customised for use in this study (24). Contact will then be made on a fortnightly basis, by phone to collect prospective health service use data in the same way. This will take approximately 15 minutes every 2 weeks. The carer will be given a diary at the time of consent to be used as an aide memoire for fortnightly data collection telephone calls from the research team. The use of this diary is optional.

Post bereavement

Post-bereavement, a follow up letter will be sent to carers to remind them that the research team will be in touch to collect further data. This letter will include information sheets about the QODD questionnaire and also about the in-depth interview.

Questionnaire

Participants will be given options to do the QODD over the phone, using an online survey tool or by post. The following outcome data will be collected at up to two time-points: immediately post bereavement (optional, carer preference at last health resource data collection telephone contact); at around 1-6 months post bereavement:

- Quality Of Dying and Death (QODD) 7 day recall, Version 1
- 2 short questions about the overall care received

Where 3 attempts to contact the participating carer by telephone have been made with no success, a paper copy of the above follow up measures will be posted to the carer for completion on one occasion only. This will be accompanied by a cover letter to explain that the research team have been unable to contact them and/or if they would prefer to complete the questionnaire at home they can do so.

Optional interview

An in depth interview will be completed by a subset of participants only and will include semi-structured interview questions. We will initially interview approximately 20 per service model type with a stopping criterion of 3 interviews with no new themes coded in order to achieve data saturation (see qualitative data analysis) [25].

If the QODD is collected by telephone, the researcher will ask the participant if they would be willing to participate in an optional in depth interview by telephone or in person to understand more about the H@H service received.

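### iPOS and the VOICES survey are listed as outcomes of the service model, but iPOS is scheduled only around entry and VOICES is not named in the data collection

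*Protocol*

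**What the plan says.** The Study Summary of the Phase 2 protocol includes, under its quantitative outcomes, "Holistic patient assessment (iPOS tool" and "Assessment of care by bereaved relatives (VOICES survey", next to the QODD and the AHCR. Section 3 repeats the list: "Secondary outcomes will include holistic patient assessment (iPOS) [21] and assessment of care by bereaved relatives (VOICES) [22", and adds service use by the AHCR. The following sentence commits the study to regression that attributes differences in quantitative outcomes to the service model. Section 3 also states: "66 patients per model type will be recruited and tracked over time (until death", with data coming from the service and the carer.

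The collection is set out in section 6. Under 6.1 the care team records background information and "the Integrated Palliative Care Outcome Scale (iPOS) questionnaire (staff version), phase of illness and modified Karnofsky score". On timing it says: "These data will be collected at the point of entry to the H@H service or within 24 hours of consent". Under 6.2 the fortnightly calls to the carer gather service use with the AHCR. After bereavement the outcome data are the QODD and "2 short questions about the overall care received".

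Section 8.2 describes a regression for the QODD alone. It adjusts for socio-demographic, clinical and carer characteristics by backward elimination from a covariate set that the team has agreed.

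**The concern.** Objective 1 is the impact of service models on patients and carers. A measure can show impact only if it is taken after the model has had time to act, and a named instrument can be reported only if it is administered. On the written schedule, iPOS fails the first test and VOICES cannot be shown to pass the second.

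Sites are chosen purposively and patients are not randomised to models, so differences in who is referred are expected. An entry score compared between models and labelled an outcome would present those differences as an effect of care. Section 11 promises guidelines on which models work best, so the mislabelling could reach commissioners. A statistical analysis plan can define scores and models, but it cannot supply later iPOS scores or VOICES items that were never collected.

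**Working it through.** The main check sets the outcome lists beside the schedule and the analysis section.

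| Listed secondary outcome | Where collected | When | Analysis named in section 8 |
|---|---|---|---|
| iPOS | 6.1, staff version | once: entry, or within 24 hours of consent | none |
| VOICES survey | not named in section 6; two overall-care questions in 6.2 | after bereavement | none |
| AHCR (service use) | 6.2 | up to two months back, then fortnightly | 8.4, descriptive costs |

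**Step 1, iPOS.** There is one time point around entry and none later. The fortnightly contacts are with carers and concern service use. The statement that patients are tracked until death has no repeat patient assessment behind it in the text. The expected difference between two models in this score is

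difference = (case-mix difference at entry) + (effect of any care given before the assessment).

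Care given after the assessment, which is nearly all of the care under study, does not enter.

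**Step 2, VOICES.** The name appears in the Study Summary, in section 3 and its reference, and in Phase 1 section 9, where the steering committee is described. It does not appear in section 6 or section 8. The post-bereavement letter encloses information on the QODD and the interview only, and the final follow-up letter concerns the interview only. The two questions on overall care have no stated source or scoring.

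**Step 3, count.** Three secondary outcomes are listed. One (AHCR) is collected under its own name and after entry. 3 − 1 = 2 are not.

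**Step 4, primary outcome.** Section 8.1 uses a difference of 10 and an SD of 16.41. It states neither alpha nor power, so two-sided 0.05 and 80% are assumed. The two-sample t-test then needs 43.25, rounded up to 44 per model type. Allowing for drop-out, 44 / (1 − 0.33) = 65.7, rounded up to 66. Both plan figures are reproduced, and neither depends on iPOS or VOICES.

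**Step 5, cost of keeping the entry measures in the QODD model.** An iPOS total and Karnofsky, each entered linearly, take 1 degree of freedom apiece. Phase of illness with k categories takes k − 1. The total is k + 1, against 4 × 44 = 176 evaluable QODD scores if all four model types are filled.

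**The case against.** The other side has several fair points.

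- **The two questions may come from VOICES.** Section 3 describes that outcome as bereaved relatives' assessment of care, and 6.2 asks bereaved carers about overall care. A reader might infer that VOICES is not collected at all. The text does not support that; it supports only that the survey is listed and that two questions of unstated source are scheduled.
- **Some care may precede the iPOS.** Patients are approached on admission by the service's own staff and given time to consider, and the form may follow consent by up to 24 hours. Section 8.4 reports that 6% of patients in a previous study died within 2 days of referral, so a day is not trivial for everyone. A reader might infer that entry iPOS carries no effect of care whatever. That goes too far; it mainly reflects case mix.
- **Case-mix adjustment is planned.** Section 8.2 controls for clinical features, and the entry measures are obvious candidates. Their not being listed by name is no fault in itself. What stands is narrower: backward elimination could remove them.
- **Section 8.2 specifies no iPOS regression.** That is true, but the general sentence in section 3 covers the quantitative outcomes, and the Study Summary counts iPOS and VOICES among them. The inconsistency remains.
- **Figure 2 and the study diagram are not reproduced in the text available.** They might show a further assessment. If so, they would conflict with 6.1, and the two would still need reconciling.

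Two other inferences also fail. No comparison with VOICES norms is planned, so none is at risk. The economic analysis is descriptive with a Mann-Whitney comparison, so there is no cost model that lacks covariates.

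**Conclusion.** The protocol is wrong as written on this point. Two of its three listed secondary outcomes are not matched by the written schedule. A comparison of entry iPOS between models would show mainly whom each model admits, and the schedule as written would not yield a result that could be called the VOICES survey.

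This should be corrected before results are reported, because relabelling is cheap and an analysis plan cannot repair it. It does not touch the primary outcome or its sample size. The conclusion rests on the text of sections 3, 6.1, 6.2 and 8.2, and on the assumption that the missing figures add no later iPOS or VOICES administration. No numerical bias can be given, since the documents contain no iPOS distributions by model.

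**What to change.** 1. In the Study Summary and section 3, move entry iPOS from the outcomes to the baseline measures.
2. In section 8.2, keep entry iPOS, phase of illness and Karnofsky in the QODD regression as case-mix covariates that backward elimination may not remove.
3. In both outcome lists, replace the VOICES survey with the two overall-care questions actually asked. State their source, and do not report them as the VOICES survey.
4. Check Figure 2 and the study diagram against the revised text.

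The cost is protocol wording and the k + 1 degrees of freedom shown above. No collected data are lost, and the study gives up only outcome claims that its schedule cannot support. Adding an iPOS after entry would be the alternative if it is to remain an outcome, but that means new data collection and cannot recover patients already followed to death.

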4. STUDY SITES

The findings from phase 1 were used to create a H@H service model typology comprising 4 model types (see Figure 1). This forms a sampling framework to select case study sites from H@H services in England (ideally from hospices responding to the phase 1 survey). Each type of H@H service within the typology will be represented by one or more case study sites. We also anticipate that the sample will incorporate geographical spread, mixture of deprivation populations and include services that are innovative or more traditionally delivered. Case study sites will be invited by the Chief Investigator to participate.

Figure 1: H@A service model typology

5. PARTICIPANT ENTRY

5.1 PATIENT CONSENT

Patients within the case study sites will be invited to participate in the study when they are admitted to the H@H service. For the purposes of this study, the definition of Hospice at Home Service is a service with the following characteristics:

- Aims to enable patients to be cared for and die in their place of choice if that is their own home:
- Employs "specialist" staff with high levels of palliative care experience;
- Ability to provide more staff time with the patient than pre-existing/other services.

Local hospice at home service staff e.g. registered nurses or health care assistants (or research nurse if they have one) will introduce the study to the patient. A patient information sheet will be given to the participants and sufficient time allowed to read the information and ask any questions they may have. If needed, the information sheet can be read out to the patient. The local hospice at home service staff member will then gain the patient's consent, using the study patient consent forms. A copy of the information sheet and consent form will be given to the patient and/or their carer, a copy filed in the patients' medical notes and a copy filed in the study site file.

Due to the nature of the patient population who will be close to the end of life, it is anticipated that some of the potential participants will be unable to provide informed consent (due to impaired cognition / impaired consciousness). For this reason a variable consenting process, involving consultee assent, will be used. The local hospice at home service team will decide and proceed using one of the options below:

- If the patient is deemed to have capacity by the local team, then consent will be sought from the patient in the normal manner.
- If the patient is deemed not to have capacity, then a personal consultee (i.e. someone who has a role in caring for the person who lacks capacity or is interested in that person's welfare

- but is not doing so for remuneration or acting in a professional capacity) will be approached for advice regarding the patient entering the study. In this study, the personal consultee could be a relation of the person, or a friend of the person.
- If the main carer or personal consultee is not available at the best time to approach the patient, a nominated consultee will be approached for advice regarding the patient entering the study. In this study, the nominated consultee could be a clinically qualified member of the patients care team who will not be involved in patient consent or involved in study procedures (i.e. patient data collection).

Where a personal or nominated consultee is used, they will be given an information sheet about being a consultee and the patient information sheet. They should be given appropriate time to read the information and have the opportunity to ask questions about the study, and asked whether in their opinion the patient would have any objection to taking part in the study. The local service staff member will then gain a declaration from the consultee, using the study consultee declaration form, if they agree that the patient would be willing to participate in the study.

Full training on the study and the informed consent process will be provided to local care staff involved in the study prior to the start of recruitment at the case study site.

